4.10 Secondary Variables

Percentage change in target ulcer depth and volume over the 12-week treatment period (Key Secondary)

The primary analysis and accompanying summaries relating to change in target ulcer area will be repeated separately for both the change in target ulcer depth and volume over the 12-week treatment period with a single exception. The initial models will include baseline ulcer depth and volume respectively for the two key secondary objectives rather than baseline ulcer area as detailed in the primary analysis.

The baseline depth, final depth, absolute change in depth and percentage change in ulcer depth over the 12-week treatment period will be summarized separated by treatment, centre, wound type and baseline depth (<median/>=median). Further summaries will be produced separated by the covariates used in the final model. The ulcer depth, change in depth and percentage change in depth will be summarized by Study Visit (2-12) and treatment, centre, wound type and baseline depth (<median/>=median). Summaries will utilize the Per Protocol Population and will be repeated for the Full Analysis Set. The summaries detailed for ulcer depth will be repeated for the target ulcer volume.

Proportion of subjects achieving confirmed target ulcer closure over the 12-week treatment period

The proportion of subjects achieving confirmed target ulcer closure, either by surgical intervention or secondary intention, over the 12-week treatment period will be analyzed as follows using the Full Analysis Set. An initial logistic regression model will contain covariates for treatment, center, wound type, baseline (defined as Study Visit 1) ulcer area and duration of ulcer. Pooling of centers with less than 10 subjects will be performed as described in the primary analysis. A forward selection procedure will be used for the addition of other baseline covariates with an F-value to attain a significance level of 0.1. Further baseline covariates to be assessed as

part of this procedure include: subject age, body mass index, baseline ulcer depth and baseline level of exudate.

The resulting analysis presented will correspond to the final model from the forward selection procedure. The results for the initial model will also be presented. For each of the effects in the initial and final model, the p-value, odds-ratio and corresponding 95% confidence interval will be presented. Secondary subgroup analyses may be conducted as a result of the covariate analyses. Additionally, treatment will be fitted on its own in a further logistic regression model. In each case, the residuals will be examined for outliers using influence plots of diagnostic statistics (Hat Matrix Diagonal, Pearson residuals, Deviance residuals, DFBETAs, C and CBAR, DIFDEV and DIFCHISQ). For each model, overdispersion will be tested for by examining the deviance and pearson statistic divided by their degrees of freedom. If these are not approximately equal to 1 then an adjusted analysis may be used for overdispersion using quasi-likelihood methods.

Cross-tabulations of each of the covariates (continuous covariates will be categorized for purposes of the cross-tabulations) with treatment and closure, will be generated for each of the baseline covariates included in the final model.

The 95% confidence interval (unadjusted for all covariates) for the difference between treatments in terms of the percentage healed by 12 weeks will be generated along with the Chi-square test p-value using the Per Protocol Population.

Two separate sensitivity analyses will be performed to ensure that the efficacy findings are not reliant on assumptions made in either the analysis or derivations; the analysis for the proportion of subjects achieving confirmed ulcer closure will be repeated with the following modifications using the Full Analysis Set only:

- 1) Worst case: In cases where subjects had missing data over the confirmatory target ulcer closure period (1 week follow-up) and it is unknown whether the closure is confirmed, these will be imputed as: Confirmed Closure=No.
- 2) Best Case: In cases where subjects withdraw from the study prior to the end of the 12-week treatment period (except in cases where the ulcer has closed), the following will be imputed: Confirmed Closure=Yes.

Whether confirmed closure was achieved will be summarised by Study Visit (Note: initial observation of closure will be summarized not the visit where closure was confirmed). The wound status (open/closed/re-opened) will be summarized for the Study Visit 14 assessment.

Whether the wound is closed (not confirmed), if so the method (surgical or secondary intention), and method of surgical closure if appropriate, and the treatment to be received post-closure will be summarised by Study Visit

Time (days) to achieve confirmed target ulcer closure by surgical intervention or secondary intervention

A proportional hazards survival analysis will be applied to the time to achieve (confirmed) target ulcer closure using the Full Analysis Set. An initial proportional hazards model will include the covariates for treatment, center, wound type, baseline (defined as Study Visit 1) ulcer area and duration of ulcer. Pooling of centers with less than 10 subjects will be performed as described in the primary analysis. A forward selection procedure will be used for the addition of other baseline covariates with an F-value to attain a significance level of 0.1. Further baseline covariates to be assessed as part of this procedure include: subject age, body mass index, baseline ulcer depth and baseline level of exudate. The resulting analysis presented will correspond to the final model from the forward selection procedure. The results for the initial model will also be presented. For each of the effects in the initial and final model, the p-value, hazard-ratio and corresponding 95% confidence interval will be presented. Secondary subgroup analyses may be conducted as a result of the covariate analyses. Additionally, treatment will be fitted on its own in a further proportional hazards survival analysis.

In each case, the assumption of proportional hazards will be verified using plots of the log cumulative hazard against log time for each treatment and each of the other factors and by assessing the treatment x time interactions. If the model assumptions of a proportional hazards do not hold such that the log cumulative hazard plots against log time are not parallel, the time interactions are significant ($p < 0.05$) or if $N < 40$ and an expected frequency of at least one cell is < 5 then a Log Rank Test may be applied. The preceding analysis will be repeated using the Per Protocol Population.

Kaplan-Meier plots will be presented by treatment and wound type, baseline ulcer area strata, ulcer duration (categorized) and also to represent all covariates with significant effects in the final survival analysis model. Individual plots for multiple factors will be generated where appropriate.

In addition, a sensitivity analysis will be performed to ensure that the efficacy findings are not reliant on assumptions made in either the analysis or derivations. For purposes of the sensitivity analysis, the time to confirmed closure for those subjects discontinuing the treatment period prematurely, will be censored at the maximum possible duration of treatment under the study protocol (84 days), rather than time of actual discontinuation. Lastly, the two sensitivity analyses defined in the proportion of subjects achieving confirmed closure analysis will be repeated for the time to confirmed closure, in these cases the censoring flag may be modified as detailed previously, but the time in days will remain unchanged.

Change in subject reported Quality of Life (QoL)

The instruments used to assess subject reported Quality of Life will be the Cardiff Wound Impact Schedule (CWIS) and the EQ-5D. All analyses relating to Quality of Life assessments will be performed using the Full Analysis Set.

Cardiff Wound Impact Schedule

The parameters for each of the domains of the CWIS questionnaire (Wellbeing, Physical symptoms and daily living, Social life) in addition to Overall HRQoL and Patient Satisfaction with overall HRQoL at baseline and end of treatment will be summarized using frequency distributions which will detail the number and percentage of subjects which fall into each category. The change in the CWIS score for each of the domains between baseline and end of treatment will be summarized.

A two sample t-test will be used to test for a difference in the mean change in CWIS score between treatments for each of the domains separately. 95% confidence intervals will also be presented. If the assumptions of the t-test are violated, the Wilcoxon rank sum test will be used instead with Hodges-Lehmann estimates of the median difference and 95% confidence interval reported.

As a sensitivity analysis, the above analysis will be repeated with any missing values coded using LOCF.

EQ-5D

Subject responses to the EQ VAS scale and derived Time Trade-off (TTO) indexes and domain averages at each assessment are continuous variables and will be summarized.

The change in EQ VAS and derived TTO index between the Randomization Visit and the End of Treatment period will also be summarized. A two sample t-test will be used to test for a difference in the mean change in EQ VAS between treatments. 95% confidence intervals will also be presented. If the assumptions of the t-test are violated, the Wilcoxon rank sum test will be used instead with Hodges-Lehmann estimates of the median difference and 95% confidence interval reported. This analysis will be repeated separately for the change in TTO index.

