3. STATISTICAL CONSIDERATIONS

3.1 DETERMINATION OF SAMPLE SIZE

The study is intended to test for non-inferiority in the percentage change in target ulcer area between PICO and tNPWT over a 12-week treatment period. During a review of five previous studies with venous leg ulcer and diabetic foot ulcer, with treatment of PICO or tNPWT, the mean percentage change in ulcer area was found to be approximately between 47-62%, in cases where it was considered an appropriate measure, the standard deviation ranged approximately between 21-24.5%. Using a non-inferiority margin of 12.5%, a sample size of 128 subjects will provide 80% statistical power at the (cumulative) 0.025 one-sided significance level assuming a weighted average mean healing of 60% with a worst case standard deviation of 24.5%. This was calculated using EAST 6. To allow for a 20% drop out rate throughout the 12-week treatment period, a total of approximately 160 subjects (80 per treatment) will be randomized.

The sample size randomized will include a minimum of 100 VLU to allow for a minimum of 70% power for VLU-only analysis using the above assumptions.

An interim analysis (built into the sample size) of key variables will take place after approximately 50% of target recruitment (80 subjects completed) with the stipulation that the interim will contain at least 40 VLU and 20 DFU. A recommendation may be made at this point to stop the trial prematurely due to efficacy or futility.

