4. ANALYSIS PLAN

4.1 General

Smith & Nephew Wound Management Global Medical and Clinical Affairs will conduct data management and statistical analysis. Unless otherwise stated, all significance tests will be two-sided tests at the 5% significance level. P-values will be quoted and 95% confidence intervals will be generated where appropriate. All p-values will be rounded to three decimal places, p-values less than 0.001 will be presented as '<0.001' in all tables.

All descriptive statistics will be summarized by treatment (PICO or ActiV.A.C.®) and by target ulcer type (Venous Leg Ulcer or Diabetic Foot Ulcer) and combined ulcer types. All summaries will be repeated separately by site. In addition, all wound progress summaries [primary variable, proportion of patients (and time to) achieve

confirmed closure] for the ActiV.A.C.® treatment arm will be separated by predominant therapy used, either continuous or intermittent therapy, and overall.

Modifications to this summary approach, including additional variables of separation, will be defined where necessary in the following sections.

Subjects are able to be re-screened up to a maximum of two times in the case of screen failure. This results in a maximum of three screening periods (Run-In Visit 1:Run-In Visit 2) per subject. In the case of multiple screening periods being conducted, unless otherwise stated, the following summaries should include only the last screening period conducted for a given subject. Unless otherwise defined, baseline is defined as Study Visit 1.

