15. The change in target ulcer area during the screening period will be derived as (change in depth and volume will be derived using the same method):

$$Area_{Run-In\ 2} - Area_{Run-In\ 1}$$

16. The percentage change in target ulcer area during the screening period will be derived as (percentage change in depth and volume will be derived using the same method):

$$\left(\frac{Area_{Run-In\ 2} - Area_{Run-In\ 1}}{Area_{Run-In\ 1}} \right) \times 100$$

17. Target ulcer area is defined as surface area as measured by the ARANZ Silhouette Device at each study visit by the Investigator. For each study visit, the change in target ulcer area will be derived as (change in depth and volume will be derived using the same method):

$$\text{Change in target ulcer area at Study Visit } n = Area_{SVn} - Area_{SV1}$$

18. For each study visit, the percentage change in target ulcer area will be derived as (percentage change in depth and volume will be derived using the same method):

$$\text{Percentage change in target ulcer area at Study Visit } n = \left(\frac{Area_{SVn} - Area_{SV1}}{Area_{SV1}} \right) \times 100$$

For purposes of the primary analysis, the percentage change in target ulcer area will be derived as using LOCF within the 12-week treatment period. The percentage change in depth and volume will be derived using the same method.

19. The time to achieve confirmed ulcer closure in days will be derived as follows:
- For those subjects that achieve confirmed closure (derived variable 20):
Date of Study Visit where closure is first recorded – Date of Randomization
 - For those subjects that achieve closure but do not achieve confirmation (derived variable 20):
Date of Study Visit where closure is first recorded – Date of Randomization
 - For those subjects that do not achieve closure during the 12-week treatment period or withdraw early, the time to achieve confirmed ulcer closure will be defined as either: Date of last study visit attended – Date of Randomization;
Or 84 days, whichever occurs earlier.

20. Whether confirmed ulcer closure was achieved will be derived as follows:

- Ulcer Closed/Ready for surgical closure=Yes at last attended Study Visit i, Ulcer Closed=Yes at Follow up assessment (Visit 14). Confirmed Closure = Yes
- Ulcer Closed/Ready for surgical closure =Yes at last attended Study Visit i, Ulcer Closed=No at Follow up assessment (Visit 14). Confirmed Closure = No

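### The closure model's overdispersion check cannot measure dispersion in one-per-subject yes/no data, and the optional correction it triggers can rescale the standard errors of a correct model.

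*SAP*

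**What the plan says.** SAP 4.3 (derived variable 20) sets out how the outcome is formed: "Whether confirmed ulcer closure was achieved will be derived as follows". Each subject receives a single status of yes, no or missing.

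SAP 4.10 then specifies the model: "An initial logistic regression model will contain covariates for treatment, center, wound type, baseline (defined as Study Visit 1) ulcer area and duration of ulcer". Area and duration are continuous, and forward selection may add more covariates. A second model follows: "Additionally, treatment will be fitted on its own in a further logistic regression model".

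The dispersion rule covers all of these: "overdispersion will be tested for by examining the deviance and pearson statistic divided by their degrees of freedom". The action is: "If these are not approximately equal to 1 then an adjusted analysis may be used for overdispersion using quasi-likelihood methods". The section does not mention grouping the data, sets no limit for closeness to 1, and does not say whether the deviance or the Pearson statistic supplies the scale. The two closure sensitivity analyses repeat the same analysis, so the rule carries over to them.

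Protocol 10.3.2 has no overdispersion rule for this endpoint and refers diagnostic detail to the SAP, so the SAP text governs.

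**The concern.** Overdispersion means more variance than the binomial mean allows. A single independent yes/no result has variance p(1−p), fixed by its mean, so there is no excess to find. With continuous covariates nearly every subject has a unique covariate profile, and each row is a binomial with one trial. On such data deviance/df has no general expected value of 1, so comparing it with 1 says nothing about whether the model is adequate.

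At stake are the p-value and 95% CI of the treatment odds ratio for a secondary endpoint. They could be narrowed or widened by a factor unrelated to the quality of the fit. The choice would be made after the data are seen, in an open-label trial that the sponsor analyses, with no threshold and no named scale.

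**Working it through.** **Inputs**
- Outcome: one status per subject (SAP 4.3).
- Reference value for both ratios: 1 (SAP 4.10).
- Sample size: "a total of approximately 160 subjects (80 per treatment) will be randomized" (SAP 3.1). This reproduces: 128/(1 − 0.20) = 160.
- Level: "all significance tests will be two-sided tests at the 5% significance level" (SAP 4.1), so z = 1.960.
- Closure rate: an assumption, because no planning value is given. The range is 5% to 90%. The 68% healed in Protocol 4.2 comes from an uncontrolled series of mostly surgical wounds and serves only as one point in that range.

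**Step 1: what the deviance contains.** For ungrouped binary data, D = −2Σ[y ln p̂ + (1−y) ln(1−p̂)]. At the logistic maximum-likelihood fit the score equations make Σ y·logit(p̂) equal to Σ p̂·logit(p̂). Hence D = −2Σ[p̂ ln p̂ + (1−p̂) ln(1−p̂)]. Given the fitted probabilities, the individual outcomes drop out, so D carries no separate information on dispersion.

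**Step 2: treatment-only model, no treatment effect.**
- D/df = [N/(N−2)] × {−2[p ln p + (1−p) ln(1−p)]}.
- At p = 0.10: −2[0.10(−2.3026) + 0.90(−0.1054)] = 0.650, and 0.650 × 160/158 = 0.658.
- Pearson: within each arm the squared residuals sum to n·p̂(1−p̂). Dividing by p̂(1−p̂) gives n, so the total is N and Pearson/df = 160/158 = 1.013 at every closure rate.

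**Step 3: effect of rescaling by the deviance.** The CI width factor (log-odds scale) is √(D/df), and two-sided type I error = 2[1 − Φ(1.960 × factor)]. At 10%: √0.658 = 0.811, 1.960 × 0.811 = 1.590, error 0.112.

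| Closure | D/df | Width factor | Type I error if scaled |
|---|---|---|---|
| 5% | 0.402 | 0.634 | 0.214 |
| 10% or 90% | 0.658 | 0.811 | 0.112 |
| 20% or 80% | 1.013 | 1.007 | 0.049 |
| 30% | 1.237 | 1.112 | 0.029 |
| 50% | 1.404 | 1.185 | 0.020 |
| 68% | 1.270 | 1.127 | 0.027 |

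At N = 128 the width factors are almost the same (0.813 at 10%, 1.187 at 50%). Pearson scaling multiplies width by √1.013 = 1.006.

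**Step 4: covariate model.** A correctly specified model with no treatment effect was simulated, 2,000 trials per scenario, N = 160. Assumptions: six pooled centers, wound type, two continuous covariates, and a linear-predictor SD of 0.5 (weak), 1.0 or 2.0 (strong). Selected rows:

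| Covariates | Closure | Mean D/df | Type I error, unscaled | Deviance-scaled | Pearson-scaled |
|---|---|---|---|---|---|
| Weak | 10% | 0.647 | 0.049 | 0.127 | 0.051 |
| Weak | 30% | 1.179 | 0.049 | 0.037 | 0.044 |
| Weak | 50% | 1.346 | 0.059 | 0.033 | 0.053 |
| Strong | 10% | 0.421 | 0.054 | 0.248 | 0.122 |
| Strong | 20% | 0.643 | 0.061 | 0.142 | 0.077 |
| Strong | 50% | 0.919 | 0.064 | 0.078 | 0.066 |

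Over all 15 scenarios, type I error is 0.049 to 0.064 unscaled and 0.032 to 0.248 with deviance scaling. With Pearson scaling it is 0.044 to 0.066, apart from the 0.077 and 0.122 shown. At 10% closure, 34% to 37% of fits failed or gave extreme estimates and were excluded, so those rows are conditional on a usable fit.

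**Step 5: would grouping rescue the check?** No. Grouped by arm, the treatment-only model has two binomials and two parameters, hence 0 df. The covariate models have about one subject per profile.

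**The case against.** The case against a serious finding has real force on size.

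- **The adjustment is permitted, not required.** A reader might infer that the SAP will rescale the standard errors. Its wording is optional, so it can do so and need not. This stands.
- **The named purpose is overdispersion.** On that reading only ratios above 1 lead to action. Intervals can then only widen, and type I error cannot exceed the unscaled rate. The inflated errors for deviance ratios below 1 need the two-directional reading, which the trigger sentence allows but does not clearly intend. This stands.
- **The trigger refers to both ratios.** If both must depart from 1, the treatment-only model would not be adjusted under any reasonable limit, because its Pearson ratio is always 1.013. This stands as a limit on how often the rule acts, but the text does not say that both are needed.
- **The scale is unnamed.** With a Pearson scale the harm is small in most scenarios. This stands, with strong covariates at low closure as the exception.
- **Direction is not simple.** A reader might infer a loss of power at any closure rate of 30% or more. With deviance scaling that reverses above about 80% closure, and with strong covariates it can reverse at mid-range rates too: 50% closure gives 0.078 against 0.064 unscaled.
- **Other closure analyses are untouched.** SAP 4.10 also plans an unadjusted difference with a chi-square test, and proportional hazards for time to closure.

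None of this makes deviance/df a measure of dispersion for these data. One might defend the check as a guard against extra variation between centers. It could not show this: Step 1 applies to the deviance whatever the cause, and in the treatment-only model the Pearson ratio is fixed by N.

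**Conclusion.** The diagnostic is wrong as written, and the correction it permits can alter the standard errors of a correct model. That conclusion needs no assumed closure rate.

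The size does. It depends on the closure rate, the strength of the covariates, which statistic supplies the scale, and whether ratios below 1 are acted on. The documents fix none of these. The larger type I errors should be read as the consequence of one permitted reading: deviance scaling applied in both directions.

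A reader might also infer a threat to the trial's main conclusion. The documents do not support that. The non-inferiority analysis of ulcer area (SAP 4.9) and the interim rule (SAP 3.3) do not use these models, closure is not a key secondary endpoint, and rescaling leaves the odds-ratio point estimate unchanged. Severity is should-fix.

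**What to change.** In SAP 4.10, delete the two overdispersion sentences. State that the scale parameter is fixed at 1, with no rescaling of standard errors, for all closure logistic models: initial, final, treatment-only and both sensitivity analyses.

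If a check of fit is wanted, compare observed with predicted closure by decile of fitted probability, or use a Hosmer-Lemeshow type test, and state that the result does not alter the standard errors. If variation between centers is the worry, model it directly.

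The cost is two sentences removed and one added, with no new data and no burden on subjects.

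### The SAP's only remedy for non-proportional hazards in time to closure is an optional, unspecified log-rank test, which does not address a non-proportional treatment effect and, if unstratified, gives up covariate adjustment

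*SAP*

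**What the plan says.** SAP section 4.10 fits a Cox model to time to confirmed closure with treatment, center, wound type, baseline area and ulcer duration, plus any forward-selected covariates. A second Cox model contains treatment alone. For the initial and final models, hazard ratios with 95% CIs are to be presented, and this is not made conditional on the diagnostics.

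Proportionality is assessed with "plots of the log cumulative hazard against log time for each treatment and each of the other factors". The only formal check named is made "by assessing the treatment x time interactions". Three conditions lead to the remedy:

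- the plots: "If the model assumptions of a proportional hazards do not hold such that the log cumulative hazard plots against log time are not parallel";
- time interactions significant at the 5% level;
- a total below 40 together with "an expected frequency of at least one cell is < 5".

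The remedy is "then a Log Rank Test may be applied". The sentence does not say which factor's plot or interaction counts, whether the test is stratified, whether it stands beside the Cox result or replaces it, or what estimate goes with it. Protocol section 10.3.2 contains no remedy of its own and refers to the SAP for assumptions and diagnostics. Kaplan-Meier plots by treatment and wound type are produced in any case.

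**The concern.** Two different problems can set off the same response, and the response suits neither well.

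If the treatment effect changes over time, the log-rank test weights the data as the treatment-only Cox model does. It has the same weakness and brings no estimate. A reader would still have only a hazard ratio that averages over a changing effect.

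If a covariate is the problem, stratifying on it removes the violated assumption while keeping the hazard ratio and the other covariates. Wound type is a plausible candidate, because VLU and DFU enter with different size and duration limits. An unstratified log-rank test removes the assumption too, but only by giving up all adjustment.

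The choice is also left open. The trial is open-label, the sponsor's own department does the analysis (SAP section 4.1), and the plot criterion is visual. An optional test without a stated role could be added or emphasised after the results are known.

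**Working it through.** **No plan figure to reproduce.** The documents give no event count, hazard ratio or power for this endpoint. The sizing in SAP section 3.1 concerns the primary endpoint only.

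**Inputs from the documents.** About 160 subjects, 80 per arm (SAP 3.1); weekly visits (SAP 2.2); 84-day horizon and Cox covariates (SAP 4.10); two-sided 5% tests (SAP 4.1); randomization strata of wound type by size (SAP 3.2).

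**Step 1: what the log-rank test is.** At each closure time let n be at risk, n1 of them on PICO, with d closures, d1 on PICO.

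- Log-rank: U = Σ(d1 − d·n1/n), V = Σ d·(n1/n)(1 − n1/n)(n − d)/(n − 1).
- Cox with treatment only, at β = 0: score U = Σ(x − p), information I = Σ p(1 − p), where p = n1/n and x is 1 for a PICO closure and 0 otherwise.

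Without ties d = 1, the last factor of V is 1, and the two agree term by term. On one simulated untied data set of 160, both gave U = −1.3214 and variance 20.4951, so χ² = 1.3214²/20.4951 = 0.085 either way. Weekly visits create ties, which alter the variance slightly; Step 2 includes them.

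**Step 2: rejection rates.** These inputs are assumptions: base hazard 0.0069 per day, so 1 − exp(−0.0069 × 84) = 44% closed by day 84; hazards may change at day 42; one balanced binary covariate; 800 trials per scenario (Monte Carlo standard error about 0.6 to 1.8 points). Cox here is the ordinary model with treatment and the covariate, unstratified. RMST is the difference in restricted mean time to day 84. HR is the treatment hazard ratio; arrows show the change at day 42.

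| Scenario | Log-rank | Stratified log-rank | Cox | RMST |
|---|---|---|---|---|
| Null, covariate without effect | 4.8% | 4.2% | 4.4% | 5.6% |
| Null, covariate 4× → 0.5× | 3.9% | 4.6% | 5.2% | 2.9% |
| HR 1.8, covariate 4× → 0.5× | 80.2% | 86.1% | 88.2% | 74.6% |
| HR 1.8, covariate 4× throughout | 72.8% | 88.2% | 88.9% | 73.6% |
| HR 2.5 → 0.4 | 61.4% | 61.1% | 62.2% | 88.4% |
| HR 2.2 → 1 | 68.1% | 68.1% | 68.4% | 82.4% |
| HR 1 → 2.5 | 54.2% | 54.1% | 54.8% | 18.0% |

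**Step 3: reading it.**

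- *Treatment non-proportional (last three rows).* Log-rank minus Cox is 61.4 − 62.2 = −0.8, 68.1 − 68.4 = −0.3 and 54.2 − 54.8 = −0.6 points. The remedy gains nothing.
- *Covariate non-proportional.* The unstratified log-rank test holds its level (3.9%) but loses 88.2 − 80.2 = 8.0 points against Cox. Stratifying the log-rank test recovers 86.1 − 80.2 = 5.9 of them. With this single covariate, the stratified log-rank test is the score test of the Cox model stratified by it, so 86.1% indicates what that model would give.
- *Strong proportional covariate discarded.* The loss is 88.9 − 72.8 = 16.1 points. This is the cost of also dropping covariates that were not at fault.
- *Restricted mean.* It is better in two rows and much worse in the late-effect row (18.0% against 54.2%), so it cannot be recommended for power.

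**The case against.** A reader might infer that, once proportionality fails, the SAP replaces the adjusted Cox analysis with an unadjusted test and leaves the endpoint without an estimate or interval. The documents do not support that. The test *may* be applied. Where section 4.10 intends replacement, as with the rank-sum test for CWIS and EQ-5D, it says so explicitly. The hazard ratios with 95% CIs are presented unconditionally. That the test is unadjusted is inferred from silence; a stratified version is not excluded.

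A reader might also infer that the log-rank test is invalid here or achieves nothing. That is too strong. It tests equality of the closure curves without assuming proportional hazards, and its simulated level was 4.8% and 3.9%. It is not the score test of the covariate-adjusted model under check, and leaving out a non-proportional covariate does remove that assumption.

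Three further points on the other side stand. The trigger sentence names no factor, so activation by a covariate is one reading: the plots cover every factor, but the only interaction named is treatment by time. Related estimates already exist in section 4.10: an adjusted odds ratio for confirmed closure, and a 95% CI for the difference in percentage healed by 12 weeks. And ordinary adjusted Cox, which the SAP already reports, lost no power when the covariate was non-proportional (88.2% against 86.1% for the stratified log-rank test).

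What remains is that the one stated remedy is unspecified, cannot help with a non-proportional treatment effect, and is a poorer choice than stratification when a covariate is at fault.

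**Conclusion.** The point holds as one of interpretation and efficiency for a single secondary endpoint. For a non-proportional treatment effect, the remedy repeats a model already fitted and supplies no interpretable estimate. For a non-proportional covariate, an unstratified log-rank test is valid but costs about 8 to 16 points of power against adjusted Cox. The upper figure comes from discarding a strong proportional covariate.

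Those sizes rest on assumed hazards, covariate effects and closure rates. The documents give none for this endpoint, and they do not say that VLU and DFU close on different time courses. The score-test identity needs no such assumptions.

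The clause on a total below 40 and a small expected cell is not a proportional-hazards criterion. It has no practical effect: about 160 subjects are planned, and even the interim look is at 80 completed. The primary non-inferiority conclusion is unaffected.

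**What to change.** Replace the log-rank sentence in SAP section 4.10 with text that says which factor each check refers to and what follows:

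- (a) If a covariate is non-proportional, stratify the Cox model by it (categorised if continuous), keep the remaining covariates, and report the treatment hazard ratio with 95% CI.
- (b) If treatment is non-proportional, keep the Cox result and add the difference in restricted mean time to closure to day 84 with 95% CI. State that it is there as an interpretable estimate, not to gain power.
- (c) Label any log-rank test as supplementary and stratify it by the four randomization strata.

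The small-sample clause may be deleted as tidying.

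The cost is a few lines of SAP text and code. Stratifying gives no hazard ratio for the stratifying factor, and the restricted mean is less familiar to readers than a hazard ratio.
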